6.6.2 Handling of Participant Withdrawals or Termination

Every effort will be made to undertake the protocol-specified safety follow-up procedures to capture AEs, SAEs, and UPs. The investigator will attempt to obtain at a minimum survival data on all participants lost to follow-up. If a participant is lost to follow-up, the study team will attempt to contact the participant 3 times by telephone and twice by email. If the participant fails to respond, locators identified by the participant at screening will be contacted in the method specified by the participant. If participants withdraw, are terminated, or are lost to follow-up prior to the end of the 8-week treatment phase (prior to T7), they will not be replaced to allow for 40 participants to complete the 8-week treatment phase (through T7), and their partial data will be handled according to the statistical analysis plan (SAP).

CONFIDENTIAL

This material is the property of the NYU School of Medicine and Langone Health
Do not disclose or use except as authorized in writing by the study sponsor

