5.1 Description of Study Design

The proposed study is a phase I/II, single-center, double-blind, randomized proof-of-concept study designed to assess feasibility and contrast effects of CBD treatment to those of placebo on drinking-related outcomes in patients with alcohol use disorder (AUD). We will evaluate the safety of an extended daily CBD treatment regimen in an AUD population, assess the impact of CBD on neuropsychological and neurophysiological domains implicated in AUD, and generate preliminary data on the impact of CBD on alcohol consumption. Following screening and baseline assessments, 40 participants will be randomized in 1:1 ratio to receive either placebo or 600mg CBD/day (PO) for 4 weeks, immediately followed by 1200mg CBD/day (PO) for an additional 4 weeks (8 weeks in total). These doses are calculated to achieve the serum CBD levels reported to reduce alcohol-seeking behavior in animal studies.

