6.3 Strategies for Recruitment and Retention

Subjects will be approximately 60 women and men, age 18 or greater, with moderate to severe AUD, recruited from the public through local media advertisements, 40 of whom will be randomized and complete the treatment portion of the study. Participants will be recruited between approximately September 2019 and August 2021. Informed consent will be given at NYU SoM space occupied by the PI within Bellevue Hospital in New York, NY, following an initial telephone consent and screen to determine potential eligibility for the study. Participants will be asked to share information about their drinking and use of any other drugs, anxiety and mood, and undergo a full medical and psychiatric evaluation at screen by licensed providers. Participants will have the option of completing the initial portion of the screening visit remotely. In this case, participants will be asked to share information about their drinking and use of any other drugs, anxiety and mood, and undergo a full psychiatric evaluation by licensed providers remotely via Webex. If inclusion and exclusion criteria continue to be met following the remote portion of the screening visit, participants will be invited to undergo a full in-person medical evaluation by licensed providers to complete the screening visit.

Active recruitment will also take place through social media sources, including Facebook and Twitter, at social service agencies, community mental health clinics, community organizations, local professional organizations, residential treatment facilities, consenting support and recovery centers, regional employee assistance programs, religious organizations, cultural centers, social clubs, and local universities. Recruitment materials will also be posted to the laboratory's website (centerforpsychedelicmedicine.com).

Clinicians will provide study staff with names and contact info for interested patients, who will sign an

CONFIDENTIAL

This material is the property of the NYU School of Medicine and Langone Health
Do not disclose or use except as authorized in writing by the study sponsor

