6.5 Total Number of Participants and Sites

Recruitment will end when approximately 60 participants are enrolled. It is expected that approximately 60 participants will be enrolled in order to produce 40 randomized participants.

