7.1.9 Duration of Therapy

The duration of the active treatment portion of the study is 8 weeks, followed by an additional 4-week follow-up period. In order for participants to be included in the primary statistical analyses, they must complete the 8-week treatment phase of the study (through T7).

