21.4 Sample Size

We will enroll approximately 60 participants, and randomize approximately 40 participants to meet our recruitment goal (through week 8/T7). Sensitivity to detect effects with the proposed study design was calculated for each hypothesis at power = 0.95 for univariate outcomes with 40 participants in 2 groups at alpha = 0.05 for the analyses described above. Hypotheses 1a and 1c are powered to detect effect sizes of approximately $d = 0.2$. Hypotheses 2a and 2b are powered to detect effect sizes of $d = 0.2$ and $d = 0.3$, respectively. Hypothesis E (exploratory hypothesis) is powered to detect an effect size of $d = 0.6$, therefore we are only powered to detect substantial impacts on drinking outcomes for this exploratory aim.

22 Source Documents and Access to Source Data/Documents

Source data is all information, original records of clinical findings, observations, or other activities in a clinical trial necessary for the reconstruction and evaluation of the trial. Source data are contained in source documents. Examples of these original documents, and data records include: hospital records, clinical and office charts, laboratory notes, memoranda, subjects' diaries or evaluation checklists, study medication dispensing records, recorded data from automated instruments, copies or transcriptions certified after verification as being accurate and complete, microfiches, photographic negatives, microfilm or magnetic media, x-rays, subject files, and records kept at the dispensation site, at the laboratories, and at medico-technical departments involved in the clinical trial. It is acceptable to use CRFs as source documents. If this is the case, it should be stated in this section what data will be collected on CRFs and what data will be collected from other sources.

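### The plan uses 40 both for participants randomised and for participants completing, with no replacement and no drop-out allowance, so the 40 behind its sensitivity statement is reached only with essentially no drop-out

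*Combined protocol and SAP*

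**What the plan says.** **Forty as the number randomised.** Section 5.1: "40 participants will be randomized in 1:1 ratio to receive either placebo or 600mg CBD/day (PO) for 4 weeks". Section 6.5: "It is expected that approximately 60 participants will be enrolled in order to produce 40 randomized participants". The 20 extra enrolled are there to yield 40 randomised; nothing sets them aside for loss after randomisation.

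**Forty as the number completing.** Section 6.3 describes about 60 recruits, "40 of whom will be randomized and complete the treatment portion of the study". Section 21.4 plans to "randomize approximately 40 participants to meet our recruitment goal (through week 8/T7", which counts the goal at the end of treatment.

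**Replacement.** Section 6.6.2 says of participants who withdraw, are terminated or are lost before T7 that "they will not be replaced to allow for 40 participants to complete the 8-week treatment phase (through T7". The same sentence leaves the handling of their partial data to the SAP, which section 21.1 says is still to be developed.

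**Who is analysed.** Section 7.1.9: "In order for participants to be included in the primary statistical analyses, they must complete the 8-week treatment phase of the study (through T7". Section 21.3.1 specifies linear mixed effects models with time as a within-subjects factor.

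**Sensitivity.** Section 21.4 states detectable effects at power 0.95 and alpha 0.05 with 40 participants in two groups. No drop-out rate or allowance is given anywhere, although section 6.6 foresees withdrawal, termination and loss to follow-up.

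**The concern.** Forty randomised, no replacement and a completers-only primary analysis give 40 analysed only if all 40 complete. The plan expects some loss but makes no provision for it in the number.

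Two things are at stake. The first is the basis of section 21.4: if 40 is the number randomised, the sensitivity refers to more people than section 7.1.9 is likely to admit. The second is the clarity of the stopping rule: section 6.6.2 states a rule and then a purpose that the rule defeats. Most of the text supports stopping at 40 randomised, but a sentence governing when randomisation ends should not contradict itself.

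**Working it through.** **Inputs from the documents.** Randomised: 40, in a 1:1 ratio, so 20 per arm (5.1, 6.5). Replacement: none (6.6.2). Primary analysis set: T7 completers (7.1.9). Power 0.95 and alpha 0.05 on 40 in two groups (21.4).

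**Assumptions.** The documents give no drop-out rate; 5% to 30% is shown, equal in both arms and independent between participants. They do not state sidedness; two-sided is used.

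**The plan's own figures.** The d values in section 21.4 (0.2, 0.3 and 0.6) cannot be reproduced, because the within-person correlation, the number of repeated measures and the sidedness are not stated. The check below therefore measures the relative loss from drop-out, not the absolute detectable effect.

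**Step 1: expected completers, 40 × (1 − p).**

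**Step 2: chance that all 40 complete, (1 − p)^40.** At 5%, 0.95^40 = 0.129; at 10%, 0.90^40 = 0.0148; at 20%, 0.80^40 = 0.00013.

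**Step 3: power lost.** For a two-sample t-test with n per arm, the noncentrality is d × √(n/2) on 2n − 2 degrees of freedom. With n = 20, 95% power is reached at d = 1.17, where the noncentrality is 1.17 × √10 = 3.70. Holding that effect fixed and reducing n:

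| Assumed drop-out | Completers | Per arm | Noncentrality | Power |
|---|---|---|---|---|
| 0% | 40 | 20 | 3.70 | 95% |
| 10% | 36 | 18 | 3.51 | 93% |
| 20% | 32 | 16 | 3.31 | 89% |
| 30% | 28 | 14 | 3.10 | 85% |

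**Step 4: does the loss depend on the simple test?** Under a repeated-measures group-by-time model with an assumed correlation of 0.5 and 2 or 6 time points, power at the effect detectable with 40 falls from 0.95 to 0.92–0.93, 0.88–0.89 and 0.83–0.85. The relative loss is much the same.

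**Step 5: what a true target of 40 completers would take, 40/(1 − p), rounded up.** At 10%, 44.4 → 45; at 20%, 50; at 30%, 57.1 → 58 randomised. This shows that the two meanings of 40 describe trials of different size; it is not a recommendation to enlarge the trial.

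**The case against.** - **A reader might infer that 40 analysed cannot be delivered.** The documents do not support that. It can be, if everyone completes, and section 21.4 says approximately 40, which leaves a little slack. If that is read as about 2 participants, 5% drop-out (38 completers) uses it up.
- **A reader might infer that the stopping point is wide open.** The text leans clearly one way: sections 5.1 and 6.5 fix the number randomised, and 6.6.2 rules out replacement in terms. Randomising until 40 complete would mean ignoring the word not. This is also a single-centre study, so sites cannot diverge. What stands is leftover purpose wording in 6.6.2, the completion wording in 6.3 and the T7 goal in 21.4.
- **A reader might blame drop-out for the distance between d = 0.2–0.6 in section 21.4 and d = 1.17 above.** That would be wrong: 1.17 is the simple two-sample figure with no drop-out at all. The gap is a separate matter.
- **The fall in analysed number depends on section 7.1.9, which the plan itself puts in doubt.** Section 6.6.2 expects partial data to be handled in the SAP, and the mixed models in 21.3.1 can use incomplete records. If those govern, most of the lost information returns. This is a strong point, and it means 7.1.9 must be part of the repair. The conflict over what 40 counts would remain.
- **The stakes are limited.** This is a phase I/II proof-of-concept study. The analyses for Hypotheses 1a and 1b use CBD-treated participants only (21.3.2), about 20 even with full retention, so the loss from 40 concerns the between-group hypotheses.

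**Conclusion.** The point holds as an internal contradiction with a modest numerical consequence. Forty is the number randomised in sections 5.1 and 6.5 and a completer count in 6.3 and 21.4, while 6.6.2 refuses replacement and names 40 completers as the aim. With 7.1.9 as written and no drop-out allowance, the number behind section 21.4 is reached for the between-group hypotheses only with essentially no drop-out.

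The loss is about 2, 6 or 10 percentage points from the nominal 95% power at 10%, 20% or 30% drop-out. That rests on the assumed rates, equal loss in the two arms, a two-sided test and strict application of the completer restriction. It does not make the trial uninformative. It should be corrected because the stated basis is wrong as written and the correction is cheap.

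**What to change.** 1. Use one rule in sections 6.3, 6.5, 6.6.2 and 21.4: 40 participants are randomised, randomisation stops at the 40th, and drop-outs are not replaced. This keeps the number in 5.1 and 6.5 and the explicit non-replacement in 6.6.2.
2. In 6.6.2, end the replacement statement at the word replaced and delete the purpose clause about 40 completing through T7; keep the partial-data clause. In 6.3, delete the words saying that the 40 also complete treatment.
3. In 21.4, label 40 as the number randomised. Give the expected number with T7 data and the sensitivity over an assumed drop-out range such as 10–30%, using the model behind the current figures and stating its inputs (correlation, number of measurements, sidedness).
4. Reconcile 7.1.9 with 6.6.2 and 21.3.1, so that the between-group analyses include all randomised participants with available data in the mixed models. This recovers most of the lost number.
5. Where completion is still reported, define it once: 6.6.2 and 7.1.9 end the treatment phase at T7, while 21.3.5 ends it at T8.

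Cost: wording in the four sections plus 7.1.9 (and 21.3.5 for item 5), and one recalculation. No extra participants or visits are needed. The stated sensitivity becomes slightly less favourable.

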6.7 Premature Termination or Suspension of Study

This study may be temporarily suspended or prematurely terminated if there is sufficient reasonable cause. Written notification, documenting the reason for study suspension or termination, will be provided by the suspending or terminating party to [name], NIH/NIAAA, the FDA, the DEA, and the NY State BNE. If the study is prematurely terminated or suspended, the PI will promptly inform the IRB and will provide the reason(s) for the termination or suspension.

Circumstances that may warrant termination or suspension include, but are not limited to:

- Determination of unexpected, significant, or unacceptable risk to participants
- Demonstration of efficacy that would warrant stopping
- Insufficient compliance with protocol requirements
- Data that are not sufficiently complete and/or evaluable

Study may resume once concerns about safety, protocol compliance, data quality are addressed and satisfy the sponsor, IRB and/or FDA.

7 Study Agent (Study drug, device, biologic, vaccine etc.) and/or Procedural Intervention

7.1 Study Agent(s) and Control Description

The TN-C200M2 Oral Capsules and matching placebo for this study are provided by Tilray™. The CBD is derived from cannabis and processed according to CGMP standards (see Quality Overall Summary document provided by Tilray). The active capsules will include CBD (the active ingredient) at a quantity of 200mg per capsule, as well as a mixture of surfactants, co-surfactants, co-solvents and carrier oils. The placebo capsules will contain no CBD.

7.1.1 Acquisition

The investigational product, CBD, will be imported from Tilray, which is located at [name]. The IND & DEA schedule I researcher, [name], will acquire a New York State Bureau of Narcotic Enforcement Class 9 license to import controlled substances as well as a DEA Schedule I import permit. Tilray will then obtain a DEA export permit that will allow them to ship CBD to [name]. Once all permits and licensure is in place, [name] will send a DEA 222 form to Tilray requesting the shipment of the investigational product. All shipping, importation and exportation of the investigational product will occur in line with local, state and federal regulations.

7.1.2 Formulation, Appearance, Packaging, and Labeling

The drug product to be used in this study (TN-C200LM Oral Capsule) is a formulation of CBD dissolved in a mix of surfactants, co-surfactants, co-solvents and carrier oils at a concentration of 400mg/g. The formulation is designed to act as a self-emulsifying drug delivery system (SEDDS). Hard gelatin size-zero capsules are filled with the formulation to a fill weight of 500mg, providing a single capsule dose of 200mg CBD. This product is investigational and will be acquired as described above in 6.1.1. The TN-C200M2 Oral capsules are packaged in pharmaceutical grade 100mL polyethylene terephthalate (PET) bottles and lid, with a fill of 20 capsules.

7.1.3 Product Storage and Stability

The study drug, CBD, will be stored securely by study personnel under the PI's individual schedule 1 DEA registration and New York Bureau of Narcotics Enforcement (BNE) class 7 license in accordance with all applicable laws and regulations. Additionally, a NYS BNE class 9 importer license and a DEA importer permit will be obtained prior to importation of study drug and study initiation. CBD will be stored in a double-locked

CONFIDENTIAL

This material is the property of the NYU School of Medicine and Langone Health
Do not disclose or use except as authorized in writing by the study sponsor

refrigerator. The refrigerator is located in a designated research room with limited access to the PI and study staff only, within the NYU-HHC CTSI Facility, which is located at [name]. The drug is to be stored between 2-8 degrees Celsius. It is recommended that the investigational product be reassayed at 9-months. The Principal Investigator will oversee the appropriate storage, accountability and dispensing of the study medication and all study drug administration to the patients will be done by the PI or treating co-investigators.

Tilray™ has provided stability data for RSM-CBD Lots P56/8/116, P56/8/116, p56/17/017 and P56/44/057 at 4, 25 and 40 degrees Celsius. 12-months data has been generated on the first two batches and 9-months data has been generated on the second two batches. There is no evidence of degradation for any of the samples stored at 4, 25 and 40 degrees Celsius after 9-months. Additional and detailed stability data can be found in the accompanying Quality Overall Summary (QOS) document.

7.1.4 Preparation

Because the investigational product is going to be shipped and received in its ready-for-dispensation formulation, there will not be any preparation required prior to dispensation. The study drug will be dispensed by qualified study personnel.

7.1.5 Dosing and Administration

Participants will self-administer CBD vs Placebo twice daily for a total of 600mg/day CBD vs. Placebo for the first four weeks of treatment and 1200mg/day CBD vs. Placebo for weeks 5-8 of treatment. For the first four weeks of treatment, participants will self-administer two 200mg capsules every morning following a light meal at approximately the same time of day, and an additional single 200mg capsule approximately 12 hours later following a light meal. During weeks 5-8 of treatment, participants will self-administer three 200mg capsules every morning following a light meal at approximately the same time of day, and an additional three 200mg capsules approximately 12 hours later following a light meal.

7.1.6 Route of Administration

CBD will be administered orally in capsules that each contain 200mg CBD vs. Placebo.

7.1.7 Starting Dose and Dose Escalation Schedule

All participants will receive 600mg/day CBD vs. Placebo for weeks 1-4 of treatment, unless contraindicated, and will be escalated to 1200mg/day CBD vs. Placebo for weeks 5-8 of treatment, unless contraindicated.

7.1.8 Dose Adjustments/Modifications/Delays

If participants report AEs that are determined by the PI to be treatment-related during administration of study medication and are intolerable to the participant or represent a significant risk to the participant, daily administration will be reduced by 200-400mg/day every two days until symptoms are resolved or tolerable. Dose may be titrated back up toward the full dose by 200 mg/day/week as tolerated. Individuals who cannot tolerate the 600mg dose will remain on their maximum tolerable dose during the second 4-week period of the study. Treatment will be discontinued immediately if continuing the medication places the participant at significant risk in the medical judgement of the PI.

7.1.9 Duration of Therapy

The duration of the active treatment portion of the study is 8 weeks, followed by an additional 4-week follow-up period. In order for participants to be included in the primary statistical analyses, they must complete the 8-week treatment phase of the study (through T7).

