6.6 Participant Withdrawal or Termination

6.6.1 Reasons for Withdrawal or Termination

Participants are free to withdraw from participation in the study at any time upon request. An investigator may terminate participation in the study if:

- Any clinical adverse event (AE), laboratory abnormality, or other medical condition or situation occurs such that continued participation in the study would not be in the best interest of the participant
- The participant meets an exclusion criterion (either newly developed or not previously recognized) that precludes further study participation
- The participant fails to adhere to protocol requirements

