21.1 Statistical and Analytical Plans (SAP)

A formal SAP will be developed prior to database lock and unblinding.

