21.3.2 Analysis of the Primary Endpoint(s)

For Hypothesis 1a, acute circulating levels of CBD will be assessed in CBD-treated participants 45 minutes after initial administration (T1, T4), and 45 minutes after administration of the morning dose of medication following 1 day (T2, T5), 1 week (T3, T6), and 4 weeks (T4, T7) of treatment with each dose of CBD. Additionally, circulating levels of CBD will be assessed in CBD-treated participants 12 hours after ingestion of the preceding evening dose following 1 week (T3, T6) and 4 weeks (T4, T7) of administration of each dose of CBD. Levels of CBD (mean and standard deviation) will be reported at each timepoint and effects of dose and timepoint will be evaluated. For Hypothesis 1b, circulating CBD levels (mean and standard deviation) 45 minutes after administration of the morning dose of medication following 1 week (T3, T6) and 4 weeks (T4, T7) of treatment with each dose of CBD will be reported in CBD-treated participants. For Hypothesis 1c, between-group differences on psychomotor tasks (T1-T8), cognitive measures (T3, T6) and number of adverse events (T1-T9) will be assessed.

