21.3.8 Multiple Comparison/Multiplicity

Because our primary outcomes are safety data, in which we hypothesize a null difference between treatment groups, we will not employ a correction for Type I error/alpha inflation.

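### The primary analyses admit only 8-week completers and no all-treated safety set is defined, so entry to the primary safety comparison can depend on harm

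*Combined protocol and SAP*

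**What the plan says.** Section 7.1.9 (Duration of Therapy) states: "In order for participants to be included in the primary statistical analyses, they must complete the 8-week treatment phase of the study (through T7".

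The primary analyses include safety. Section 5.1.1 lists safety among the primary endpoints. Section 21.3.2, under the primary endpoint analysis, says that for Hypothesis 1c "between-group differences on psychomotor tasks (T1-T8), cognitive measures (T3, T6) and number of adverse events (T1-T9) will be assessed". Section 21.3.8 begins: "Because our primary outcomes are safety data, in which we hypothesize a null difference between treatment groups".

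Harm can end participation or treatment. Under Section 6.6.1 the investigator may terminate participation if "Any clinical adverse event (AE), laboratory abnormality, or other medical condition or situation occurs such that continued participation in the study" would not serve the participant's interest. Section 7.1.8 provides for dose reduction when related AEs are intolerable or pose a significant risk, and adds: "Treatment will be discontinued immediately if continuing the medication places the participant at significant risk in the medical judgement of the PI".

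For people who leave before T7, Section 6.6.2 says "their partial data will be handled according to the statistical analysis plan (SAP". Section 21.1 says of that plan: "A formal SAP will be developed prior to database lock and unblinding".

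**The concern.** A safety comparison should include everyone exposed. Here a participant who has an AE and leaves because of it is removed from the analysis meant to count that AE. If affected participants leave more often than unaffected ones, the completers' event rates are too low. If that happens more on CBD, the bias favours CBD, and the observed difference moves toward zero or past it. The direction matters because the trial hypothesises no difference in safety: the rule can help produce the result that the plan expects.

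The rule is also unclear. It does not say whether someone who stops the drug but attends through T7 counts as a completer. Section 16.4 keeps follow-up going after the drug is stopped for pregnancy, and Section 21.3.5 tallies stopping the intervention and stopping follow-up as separate things. Section 7.1.9 ends the treatment phase at T7, Section 21.3.5 at T8.

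**Working it through.** **1. Does any other section override 7.1.9?**

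- Section 6.6.2 defers partial data to the SAP. It does not withdraw the completer rule, and the SAP is not yet written.
- Section 21.3.1 plans mixed models, which can use incomplete records, but 7.1.9 removes non-completers before the model is fitted.
- Section 10 covers all subjects for monitoring. It does not define an analysis set.
- Section 21.3.4 (Safety Analyses) names no analysis set, so it is unclear whether 7.1.9 governs it.
- Sections 16, 19, 21.3.5 and 21.3.9 cover reporting, DSMB review, tallies of discontinuation and AE listings. None sets the population for Hypothesis 1c.

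**2. Inputs for the size.** From the documents: 40 randomised 1:1 (Section 5.1), so 20 per arm; T3, T4, T6 and T7 fall at weeks 1, 4, 5 and 8. The plan has no figure of its own to reproduce on this point. All AE and leaving rates below are assumed.

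**3. Proportion with a given AE.** Let r be the true risk, s the share of affected participants who leave before T7, and u the share of unaffected participants who leave. The completers' rate is r(1−s) / [r(1−s) + (1−r)(1−u)]. For r = 0.20, s = 0.5, u = 0 this is 0.10/0.90 = 11.1%; for r = 0.05 it is 0.025/0.975 = 2.6%. With u = 0 throughout:

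| True risk, CBD / placebo | Affected who leave, CBD / placebo | Completers, CBD / placebo | Difference in points, true → completers |
|---|---|---|---|
| 20% / 5% | 25% / 25% | 15.8% / 3.8% | 15.0 → 12.0 |
| 20% / 5% | 50% / 50% | 11.1% / 2.6% | 15.0 → 8.5 |
| 20% / 5% | 50% / 25% | 11.1% / 3.8% | 15.0 → 7.3 |
| 20% / 15% | 50% / 25% | 11.1% / 11.7% | 5.0 → −0.6 |
| 20% / 20% | 50% / 25% | 11.1% / 15.8% | 0 → −4.7 |
| 40% / 10% | 50% / 50% | 25.0% / 5.3% | 30.0 → 19.7 |

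If unaffected participants leave at the same share as affected ones (u = s), 20% and 5% stay 20% and 5%: no bias.

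**4. Number of AEs, the endpoint that Section 21.3.2 names.** Over weeks 0 to 8, let AEs occur at rate l per week, each causing exit with probability q. Completers are those with no exit-causing AE, so their mean count is 8l(1−q). For everyone treated, the raw mean is (1−exp(−8lq))/q, and events per person-week equal l.

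- l = 0.20 on CBD and 0.10 on placebo (true means 1.60 and 0.80), q = 25% and 10%: completers 8×0.20×0.75 = 1.20 and 8×0.10×0.90 = 0.72. The difference is 0.48 instead of 0.80.
- Equal l = 0.20, q = 25% and 10%: completers 1.20 and 1.44. The difference is −0.24 instead of 0.
- In that second case the raw all-treated means are 1.32 and 1.48, still truncated by early exit, while the rates are 0.20 and 0.20.

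Simulation with 400,000 per arm agreed with the completer means (1.20, 1.44 and 0.72).

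**5. Meaning of completion.** Take 20% and 5% with half of affected participants stopping the drug, and let k be the share of those who still attend through T7 and are counted. Then s = 0.5(1−k). For k = 0, 0.5 and 1 the difference is 8.5, 12.0 and 15.0 points from the same trial.

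**6. Data discarded even without bias.** If leaving is uniform over 8 weeks, 7/8 = 87.5% of leavers have a T3 cognitive score, 3/8 = 37.5% also have T6, and 4/8 = 50% have both T3 and T4 pre-dose samples at 600 mg. If leaving falls linearly over the 8 weeks these become (7/8)² = 77%, (3/8)² = 14% and (4/8)² = 25%.

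**The case against.** The completer rule is a single sentence outside the statistics section, and Section 21 does not repeat it. The SAP is due before unblinding and could define a proper safety set. Section 7.1.8 reduces the dose first and keeps people who cannot tolerate 600 mg on a tolerable dose, so fewer affected people may leave than the scenarios assume. Most of the illustrations concern a proportion, while the plan names a count. With 20 per arm, the standard error for 20% against 5% is √(0.20×0.80/20 + 0.05×0.95/20) = 10.2 points, larger than the illustrated 6.5-point shift. AE collection, DSMB review and AE listings cover everyone, so serious related events would still be seen. Finally, using all data whether or not the drug was stopped mixes in off-drug time, which can itself dilute a difference.

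Some of this stands. The size is unknown, live monitoring is intact, and off-drug time should be shown separately. The rest does not remove the problem. A SAP that follows 7.1.9 carries the bias forward, and one that departs from it contradicts the protocol. Dose reduction narrows the route from harm to exclusion but does not close it. The count calculation shows the same bias. A bias smaller than one standard error is still a bias, and it can run in the direction of the trial's hypothesis.

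**Conclusion.** The concern holds. Followed as written, the plan conditions the primary safety comparison on a status that harm can determine, and nothing in the documents supplies an all-treated set. This is a wrong rule on a primary endpoint, not only a missing detail, and it must be changed before database lock.

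On the assumed rates, the bias ranges from none (leaving unrelated to harm) to a loss of nearly half the true difference (15.0 to 8.5 points), or a reversal that favours CBD (0 to −4.7 points; −0.24 AEs per person). These figures show direction and possible scale; they are not forecasts. The defect lies in the comparison between arms, not in AE collection or oversight.

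**What to change.** Replace the sentence in Section 7.1.9 and carry the change into the SAP:

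1. Analyse Hypothesis 1c in every randomised participant who took at least one dose, using all data collected whether or not the drug was stopped. By arm, report the AE count with follow-up time (for example as a rate by dose period) and the proportion with any AE. Show on-drug and off-drug time separately. Follow-up time is needed because Section 11 closes AE recording 7 days after participation ends: week 4 for someone who leaves at week 3, about week 13 for someone followed to T9.
2. Summarise CBD levels at each visit in every CBD participant with an evaluable sample. For Hypothesis 1a, use participants with both pre-dose samples at that dose, or the planned mixed model on all samples.
3. Keep the completer analysis as a sensitivity analysis, with one definition that separates stopping the drug from leaving the study and reconciles T7 (7.1.9) with T8 (21.3.5).
4. Report numbers and reasons for early exit by arm.

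A separate drafting point: Sections 6.3 and 6.6.2 should be reconciled on whether 40 is the number randomised or the number completing.

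The cost is protocol wording plus a SAP that is already due. The change uses data obtained before exit and the follow-up that Section 6.6.2 already commits to: "Every effort will be made to undertake the protocol-specified safety follow-up procedures to capture AEs, SAEs, and UPs". Recovery is partial. Assessments not done after exit stay missing, so anyone who leaves before T3 has no on-treatment cognitive score. A rate corrects for truncated counts only if AE risk is roughly constant within each reported period.
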